## 1. INTRODUCTION

### 1.1 MEDICAL BACKGROUND

Diabetic retinopathy can cause visual loss in a number of ways. Microvascular changes due to hyperglycemia lead to increases in permeability, thus extravascular exudation and fluid accumulation in the macula (diabetic macular edema, DME). Similarly, alterations of microvessels can lead to retinal non-perfusion and ischemia. The consequent dramatic increase of vascular endothelial growth factor (VEGF) drives the formation of retinal new vessels (proliferative diabetic retinopathy, PDR), that can eventually bleed, with a sudden decrease in vision (vitreous hemorrhage). In both conditions, VEGF plays a fundamental role, and in fact anti-VEGF agents are effective in improving both DME and PDR. In PDR, pan-retinal photocoagulation (PRP) is the current standard of care. PRP aims to destroy the ischemic retina, which is the major source of VEGF, thus it is effective in prevention and / or regression of the formation of new vessels.

In some patients, however, even in the absence of DME, after successful treatment with PRP with no evidence of active new vessels, the visual acuity continues to decrease.

Some reports have suggested that a possible explanation might be the spreading of ischemia in the central part of the retina, the macula. In this condition, called diabetic macular ischemia (DMI), the retinal tissue may not receive enough nutrients leading to retinal tissue loss and permanent and irreversible vision loss. In DMI, anti-VEGF therapy is not effective, and destructive laser photocoagulation cannot be applied.

Previously, DMI was observed and diagnosed by means of fluorescein angiography (FA) using an intravenous dye. It was defined as an abnormal enlargement of the physiologic foveal avascular zone (FAZ). In patients with diabetic retinopathy, FA might show an abnormal enlargement of the FAZ, which is the most common definition of DMI. Recently, optical coherent tomography angiography (OCTA) has emerged which can visualize the retinal blood vessels and hence ischemia in greater detail. OCTA is non-invasive and multiple levels of the capillary plexus can be visualised. OCTA is able to measure the area of the FAZ. Moreover, it was found that the FAZ measured by FA corresponds well with the superficial retinal plexus recorded by OCTA (R17-3317). For these reasons OCTA is likely to become the gold standard in the diagnosis and monitoring of DMI.

[figure not shown]
There is a large list of unknowns related to DMI. Since this condition is associated with a progressive loss of neural tissue, it can be hypothesized that restoration of the macular vasculature before retinal degeneration occurs could be a key objective for these patients and prevent permanent vision loss. There are currently no treatments available for DMI making it an urgent unmet need.

**1.2 DRUG PROFILE**

In the retina, [REDACTED] is secreted by retinal ganglion cells. In the body, [REDACTED] is secreted

[REDACTED]

#### Data from clinical studies

Twelve patients have been treated in the SRD part intravitreally with BI 764524 at the time of finalization of CTP version 3. No DLEs, drug-related SAEs or Drug-related AEs were reported.

For a more detailed description of the BI 764524, please refer to the current Investigator's Brochure (IB, [C27076166-01](#)).

#### **1.2.1 Residual Effect Period**

For BI 764524 the residual effect period (REP) after IVT administration is not known.

### 1.3 RATIONALE FOR PERFORMING THE TRIAL

Diabetic macular Ischemia (DMI) is a chronic complication of diabetic retinopathy (DR) and can potentially lead to visual functional loss. Currently, there are no approved or effective treatments to prevent either onset or progression of DMI in laser-treated PDR patients.

As a transition from preclinical investigations to clinical development in this first-in human trial, safety, tolerability and early biological response of BI 764524 will be assessed in DMI volunteer patients

This trial will include patients affected by DMI with significant visual loss since intravitreal (IVT) injections in patients without the condition would not be considered ethically justifiable.

This trial will consist of a single rising dose (SRD) part and a multiple dosing (MD) part.

In the SRD part of the trial, 3 rising doses (at least 3 evaluable patients per dose cohort) are planned to be intravitreally administered. Within each dose cohort, all patients will receive the same BI 764524 dose. The next higher dose will only be administered, if the treatment in the preceding dose cohort was safe and showed acceptable tolerability.

In the MD part, patients will be randomized to receive either active treatment or sham injection: 20 patients on active treatment and 10 patients on sham injection over a 22-week period. After an initial active treatment period of 12 weeks (3 injections/sham injections in 4 weekly intervals) patients will be followed up for an additional 10 weeks without further injections to study the treatment effect. This might also help to guide injection frequency intervals in later studies.

The MD part of the trial will provide information about the early biological response of BI 764524 by comparing the treated groups to the sham arm.

### 1.4 BENEFIT - RISK ASSESSMENT

#### 1.4.1 Benefits

DMI is a progressive disease and patients will have irreversible retinal damage if DMI is present for a long time. Degeneration of retinal tissue in the macula leads to permanent visual impairment. There is no approved treatment for this disease.

Even though pre-clinical data shows that BI 764524 can improve retinal vascularization, because of the long duration of the pathology of DMI, long-term benefit for the patients entered in this trial is unlikely. Their participation in this trial, however, is of major importance to the development of BI 764524 to determine a safe dose selection for further clinical trials in this pre-selected patient population.

Because this is the First-in-human trial with BI 764524, special attention will be applied to ensure the highest level of safety for patients selecting the starting dose, the dose escalation steps and the highest dose applied (see Section [4.1.2](#)).

#### **1.4.2 Risks**

BI 764524 has not previously been tested in humans, but based on the pre-clinical toxicology studies, no specific adverse events are expected. Patients in this trial are exposed to risks of trial procedures and risks related to ophthalmic and systemic exposure to the trial medication. Similar to other intravitreal biologic therapies, there is a risk of ocular inflammation, however, this is usually mild and reversible. Patients will be monitored for ocular inflammation and treated if deemed appropriate by the investigator. Because of the low dosage used in intravitreal BI 764524, the systemic exposure is expected to be very low and hence unlikely to have significant effect as with intravitreal anti-VEGF therapies. In a subset of patients, an optional sampling of the aqueous humor will be performed at baseline and at visits 4, 6 and 7 in the MD part. This is known as an ‘anterior chamber tap’ and requires insertion of a 30 gauge needle into the anterior chamber of the eye under topical anesthesia to remove a small amount (0.1ml) of aqueous fluid. An assay will measure the quantity of [REDACTED] in the aqueous and the results will improve our understanding of the ocular PK/PD of BI 764524.

Table 1.4.2: 1 Overview of trial related risks

Possible or known risks of clinical relevance for this trial	Summary of data, rationale for the risk	Mitigation strategy
Investigational Medicinal Product BI 764524		
Intraocular inflammation	IVT administration of BI 764524 in cynomolgus monkeys showed signs of intraocular inflammation (See IB chapter 5.3) in some animals. These findings had no impact on ophthalmic function (i.e. ERG) and was not associated with any histopathological changes and resolved during the recovery phase.	At each visit a complete ophthalmic examination will be performed to detect early signs of intraocular inflammation (see chapter 1.4.1.4)
Immunogenic response	No ADA response was observed in the 13-week IVT toxicity study. However, because this trial is the FIH application of BI 764524, potential immunogenic response can occur	ADA in serum will be evaluated at day 1 and 99 in SRD, and at day 1 and 85 in MD
Drug-induced liver injury (DILI)	This trial is FIH application of BI 764524, and even if the expected systemic exposure is anticipated to be low, any possible effect on liver function needs to be addressed	Lab tests will be performed at each visit (except day 4 in SRD)
Trial procedures		
Risks related to IVT injection	Clinical trials assessing efficacy and safety in marketed drugs administered via IVT injection showed a low rate of complications associated with IVT injection procedure (<0.1%, including endophthalmitis, traumatic cataract, and increased intraocular pressure). Because the procedure of intravitreal injection of BI 764524 is the same (use of a filter needle to extract product from the vial and same needle size for injection, 30 gauge), the expected adverse events related to the procedure are considered equal to what was observed with marketed drugs	At each visit a complete ophthalmic examination will be performed to detect early signs of complications. Intra-ocular pressure (IOP) will be measured at each visit.
Risks related to blood sampling	Blood sampling may be accompanied by mild bruising and also in rare cases, by transient inflammation of the wall of the vein. In addition, in rare cases a nerve might be injured while inserting the venous catheter, potentially resulting in paraesthesia, reduced sensibility, and/or pain for an indefinite period.	The total volume of blood withdrawn during the entire study per patient will not exceed the volume of appr. 500 mL.
Risks related to Anterior Chamber tap	Corneal abrasion, cataract formation, infection, iris and lens trauma	Only experienced physicians will undertake the procedure

#### 1.4.2.1 Available data from pre-clinical toxicity studies

##### 1.4.2.1.1 IVT administration of BI 764524

##### 1.4.2.1.2 Immunogenic response in pre-clinical studies

#### 1.4.2.2 Risks related to intravitreal injection

Intravitreal injections may have potentially serious adverse events, but these are considered rare: clinical trials assessing efficacy and safety of EYLEA® intravitreal injections showed serious adverse reactions related to the injection procedure in <0.1%, including endophthalmitis, traumatic cataract, and increased intraocular pressure ([https://www.accessdata.fda.gov/drugsatfda\\_docs/label/2011/1253871bl.pdf](https://www.accessdata.fda.gov/drugsatfda_docs/label/2011/1253871bl.pdf)). Because the procedure of intravitreal injection of BI 764524 is the same (use of a filter needle to extract product from the vial and same needle size for injection, 30 gauge), the expected adverse events related to the procedure are considered equal to what was observed with marketed drugs (e.g. EYLEA®).

BI recommends the use of material for intraocular drug delivery, which is according to standard medical practice. This material is not officially approved for intraocular drug delivery, with associated potential risks. Long-term experience as standard of medical care suggest a favourable risk-benefit profile. To the best of the sponsor's knowledge there is currently no product on the market, which is officially approved for intravitreal drug delivery.

The needles for preparation of the drug and intravitreal injection are usually silicone oil coated to ease the injection of the needle through the tissue. This carries the potential risk for a silicone oil transfer into the vitreous with the potential risks for occurrence of side effects like vitreous floaters or intraocular inflammation. The overall risk for such events is based on long-term experience with comparable material and is considered low. However, patients should be made aware of this risk, as reflected in the Informed Consent Form (ICF). To the best of the sponsor's knowledge there is currently no product on the market, which is silicone-free. The recommended syringes are silicone oil free and not considered to carry this risk.

The IMP handling instructions do not mandate the use of materials from certain manufacturers and leaves the decision to the treating investigators/sites on which materials to use if it meets the specifications as described in the IMP handling instructions for BI 764524.

#### **1.4.2.3 Risks related to blood sampling**

Blood sampling may be accompanied by mild bruising and also, in rare cases, by transient inflammation of the wall of the vein. In addition, in rare cases a nerve might be injured while inserting the venous catheter, potentially resulting in paraesthesia, reduced sensibility, and/or pain for an indefinite period.

The total volume of blood withdrawn during the entire study per patient will not exceed appr. 500 mL. No health-related risk is expected from this blood withdrawal.

#### **1.4.2.4 Planned measures for monitoring the risks**

Patients will be evaluated with functional, imaging and systemic tests to identify any possible adverse event. Specifically, any signs of intraocular inflammation will be assessed by slitlamp examination of anterior chamber, vitreous and posterior segment of the eye, to identify occurrence of flare or cells in the anterior chamber, deposits of material in the corneal endothelium, deposits on the anterior capsule of the crystalline lens, any signs of vitreous haze, vitreous cells, vitreous snowbanks/snowballs, signs of intraretinal edema or retinal thickening, signs of perivascular inflammation e.g. vessel walls sheathing, signs of incipient retinitis or intraretinal haemorrhages.

Spectral domain optical coherence tomography (SD-OCT) will be used to evaluate any possible occurrence of intraretinal cystic edema or perivascular reaction. The same imaging modality will be used to evaluate early signs of cell toxicity (e.g. increased ellipsoid zone disruption, granular appearance of outer retinal layers, increase in intraretinal foci predominantly located in the outer nuclear layers).

Additionally, a systemic evaluation will be performed at the time-points specified in the flow charts, to assess any possible systemic reaction. This will include body weight, blood pressure, heart rate with Electrocardiogram (ECG), full safety lab. The required assessments will be adapted according to the pre-clinical trial results. All these evaluations will have to be reported immediately for evaluating any possible safety issue related to the drug or to inflammatory response.

In the trial design a sentinel approach will be used in the SRD part, according to EMA and ICH guidelines (EMA/CHMP/SWP/28367/07 Rev.1; EMA/CHMP/ICH/731268/1998): for each cohort the first patient will be dosed and monitored to exclude acute AEs, before dosing the other patients of the same cohort (see Section [3.1](#)). Moreover, the duration of the observation will reflect the expected human pharmacokinetics (PK) of BI 764524, with a follow-up for all patients up to 98 days, with appropriate ophthalmologic and systemic evaluations (see Section [3.1](#)).

In addition a Safety Monitoring Committee (SMC) will be established to review individual and aggregated safety data at regular intervals to determine the safety profile and risk/benefit ratio and decide on the next dose level and the next cohort size, or the appropriacy of further enrolment (see section [8.7](#)).

#### **1.4.2.5 Drug induced liver injury**

Although rare, a potential for drug-induced liver injury (DILI) is under constant surveillance by sponsors and regulators. Therefore, this trial requires timely detection, evaluation, and follow-up of laboratory alterations in selected liver laboratory parameters to ensure patients' safety (see also Section [5.2.7.1.4](#), AEs of special interest).

### **1.4.3 Discussion**

Considering the data available from previous trials evaluating the same mode of action (MoA), and data from pre-clinical studies on BI 764524, in this trial ophthalmic and systemic examinations are planned in all the visits.

Blood tests and physical examination will evaluate potential changes in blood cell count and in any safety lab parameters, as well as in body weight and blood pressure. Ophthalmic physical examination will focus on the risks related to the procedure (e.g. endophthalmitis and retinal detachment), and the risks related to a potential immunologic response. Imaging and functional tests will further assess any possible signs of neurotoxicity after the administration of the drug.

DMI is a potentially blinding disease, with no treatment available. Given the urgent need to address this unmet medical need and considering the expected safety profile of BI 764524 based on pre-clinical evaluations, it is considered acceptable to expose the patients to the trial risks.

## 2. TRIAL OBJECTIVES AND ENDPOINTS

### 2.1 MAIN OBJECTIVES, PRIMARY AND SECONDARY ENDPOINTS

#### 2.1.1 Main objectives

The objective of this trial is to determine the maximum feasible dose (MFD) for further development of BI 764524 in patients with pan retinal coagulation treated proliferative diabetic retinopathy (PDR) patients with diabetic macular ischemia(DMI) based on the primary endpoint occurrence of dose limiting events (DLE) during MFD evaluation period of 7 days (SRD) or 28 days after last administration (MD) and to investigate the safety, tolerability and early biological response after multiple IVT injections of BI 764524.

#### 2.1.2 Primary endpoint

SRD part:

- number of patients with dose limiting events (DLEs) from drug administration till day 8 (7 days after treatment)

MD part:

- number of patients with drug related adverse events (AEs) from drug administration till end of study (EOS)

[figure not shown]
#### 2.1.3 Secondary endpoint

SRD part:

- number of patients with drug related AEs at EOS
- number of patients with ocular AEs (eye disorders) at EOS

MD part:

- change from baseline of the size of the FAZ in optical coherence tomography angiography (OCTA) in superficial and combined vascular complex at Visit 5
- change from baseline of the size of the FAZ in optical coherence tomography angiography (OCTA) in superficial and combined vascular complex at Visit 7
- change from baseline of BCVA at Visit 3
- change from baseline of BCVA at Visit 4
- change from baseline of BCVA at Visit 5
- change from baseline of BCVA at Visit 6
- change from baseline of BCVA at Visit 7
- change from baseline of Central retinal thickness (SD-OCT) at Visit 3
- change from baseline of Central retinal thickness (SD-OCT) at Visit 4
- change from baseline of Central retinal thickness (SD-OCT) at Visit 5
- change from baseline of Central retinal thickness (SD-OCT) at Visit 6
- change from baseline of Central retinal thickness (SD-OCT) at Visit 7
- number of patients with ocular AEs (eye disorders) at EOS

### 3. DESCRIPTION OF DESIGN AND TRIAL POPULATION

#### 3.1 OVERALL TRIAL DESIGN AND PLAN

This trial will consist of an SRD part followed by an MD part. SRD part will be non-randomized, open-label, and uncontrolled. MD part will be single-masked, randomized and sham-controlled.

##### SRD part:

In the SRD part, the starting dose is [REDACTED]. The other provisional dose level is [REDACTED], and the maximum planned dose is [REDACTED]. For each cohort, a single patient will be dosed on day 1, and the dosing investigator, coordinating investigator and 2 representatives of the sponsor who are involved in the trial will carefully evaluate all available systemic (i.e. physical examinations, safety lab parameters, ECG and AEs) and ophthalmologic (i.e. as defined in Section 5.2.1) safety data until day 4. If this patient neither has experienced an ophthalmologic nor a systemic serious adverse event, the remaining 2 patients will be dosed. Written minutes of this assessment are being distributed to all investigators participating in this trial.

For any dose-escalation cohort, at least 3 evaluable patients will be required. Each cohort will consist of newly enrolled patients.

A Safety Monitoring Committee (SMC, see Section 8.7) will decide on the next dose level to be investigated and on the size of the next cohort based on occurrence of DLEs and on additional information (systemic PK and patient profiles). Systemic PK data from preceding cohorts (not from the ongoing cohort) will be available for evaluation. First SMC meeting will take decision based on safety data only. Refer to figure 3.1:1 (SRD) and figure 3.1:2 (MD) for a schematic representation of the dose escalation.

A Bayesian logistic regression model (BLRM), based on a weekly informative prior distribution, and employing the escalation with overdose control (EWOC) principle (see Section 7) will be used for guiding the dose escalation [R13-4803]. After all patients in a cohort have either experienced a DLE or have been observed for at least the 7 days evaluation period without experiencing a DLE (I.e. 7 days after drug administration, until visit 4, will be evaluated per patient), the BLRM will be updated with the newly accumulated data. The overdose risk will then be calculated for each dose, and escalation will be permitted to all planned doses which fulfil the EWOC criterion and the respective escalation rule.

The BLRM provides estimates for the probability of observing a DLE for each planned dose. Dose escalation will be permitted to the next planned dose which fulfils the EWOC criterion. Note that this may also result in repeating the current dose level, or in going down to a lower dose level again.

If DLEs are observed in the first two consecutive patients of a previously untested dose level, subsequent enrolment to that cohort will be stopped.

The maximum feasible dose (MFD) is considered as reached if at least 6 patients have been evaluated at a dose level which is the model's recommendation for the next dose cohort. Note the MFD will likely be the highest feasible dose, [REDACTED], rather than the highest tolerable dose in strict sense. The MD part of the study would only start if the highest dose ([REDACTED]) is tolerated.

- After the DLE period (7 days after drug administration) is over for the last patient in the SRD part, all available trial data will be analyzed and a decision is made whether to proceed to the MD part or not. Before starting the MD part, regulatory authorities and institutional review boards (IRBs) / independent ethics committees (IECs) will be informed of the internal results of the SRD part.

[figure not shown]

Figure 3.1: 1 Schematic representation of the dose escalation process in the SRD part of the trial

MD part:

The MD part will consist of one dose cohort (N=20 on dose + 10 sham injection). The highest dose [REDACTED] if established as safe and tolerable during the SRD part will be used in the MD part after the SRD part has been completed. Patients that had received a dose in the SRD part of the trial will not be included. Patients will be randomized to receive either active treatment or sham injection.

In the MD cohort, patients will receive three consecutive doses/sham injection over a 3-month period (dosing every 4 weeks). The SMC will meet regularly to review the safety data.

In all patients included in the MD part of the trial, safety and early biological response will be studied up to 98 days after the last injection.

[figure not shown]

Figure 3.1: 2                      Schematic representation of the dosing in the MD part of the trial

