## 5.2 ASSESSMENT OF SAFETY

### 5.2.1 Dose limiting event

A DLE is defined as the occurrence of any of the following events in the study eye within the evaluation period (7 days after drug administration):

- Development of sterile endophthalmitis and/or sterile inflammation of the vitreous of grade 3+ according to the NEI Grading of vitreous haze, and anterior chamber cells of 3+ according to the Standardization of Uveitis Nomenclature (SUN) working group (WG) grading scheme (see Table 5.2.1: 1 below) and a duration of 5 or more days between day 1 and day 8
- Visual loss of more than 15 letters at any given time-point
- Persistent IOP over 30 mmHg for 3 days
- Signs of vascular occlusion in a 1st (the main branch) or 2nd degree (the vessel after the first bifurcation of the main branch) retinal vessel, including peripheral retinal hemorrhages in the area supplied by the occluded vessel (hemorrhage of the macula would not be included as this is a symptom of the disease).

Table 5.2.1: 1 The SUN Working Group Grading Scheme for Anterior Chamber Cells ([R18-1136](#))

Grade	Cells in Field 
0	<0
0.5+	1-5
1+	6-15
2+	16-25
3+	26-50
4+	>50

 Field size is a 1 mm by 1 mm slit beam.

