###### **5.2.7.1.2 Serious adverse event**

A serious adverse event (SAE) is defined as any AE which fulfils at least one of the following criteria:

- Results in death
- Is life-threatening, which refers to an event in which the patient was at risk of death at the time of the event; it does not refer to an event that hypothetically might have caused death if more severe,
- Requires inpatient hospitalisation
- Requires prolongation of existing hospitalisation
- Results in persistent or significant disability or incapacity
- Is a congenital anomaly/birth defect

- Is deemed serious for any other reason if it is an important medical event when based upon appropriate medical judgment which may jeopardise the patient and may require medical or surgical intervention to prevent one of the other outcomes listed in the above definitions. Examples of such events are intensive treatment in an emergency room or at home for allergic bronchospasm, blood dyscrasias or convulsions that do not result in hospitalisation or development of dependency or abuse

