## **6.2.2 Treatment period(s)**

For the SRD part, masking is not required for the IVT injection preparation or administration. For the MD part, IVT injection will be prepared by the unmasked pharmacist (qualified person). For the MD part, an unmasked injector with no other involvement in the trial will administer either active or sham injection according to the treatment assigned by IRT. IVT injections must be carried out according to medical standards and applicable guidelines by a qualified physician experienced in administering IVT injections and will be done as part of drug administration visit procedures (Visit 2 for SRD part and Visits 2, 3 and 4 for MD part) after the other ophthalmologic assessments in the [Flow Chart I](#) and [Flow Chart II](#) have been performed (please see Section [4.1](#) for details).

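### The day-4 sentinel review examines DLE data but holds patients 2 and 3 only for a serious adverse event, so a non-serious sentinel DLE triggers no written hold

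*Protocol*

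**What the plan says.** Under Protocol Section 3.1 (SRD part), one patient per cohort is dosed first. The dosing investigator, the coordinating investigator and two sponsor representatives then review systemic safety data and the ophthalmologic data defined in Section 5.2.1, up to day 4. The release rule reads: "If this patient neither has experienced an ophthalmologic nor a systemic serious adverse event, the remaining 2 patients will be dosed". Section 1.4.2.4 states the purpose more broadly, "for each cohort the first patient will be dosed and monitored to exclude acute AEs, before dosing the other patients of the same cohort", and refers to Section 3.1 for the detail.

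Section 5.2.1 defines a DLE as any of four study-eye events within 7 days of dosing. Two of them are "Visual loss of more than 15 letters at any given time-point" and "Persistent IOP over 30 mmHg for 3 days". The others are grade 3+ inflammation lasting 5 or more days, and signs of occlusion in a first- or second-degree retinal vessel. Section 5.2.7.1.4 classes DLEs as adverse events of special interest. That brings 24-hour reporting but no hold on dosing.

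Three other rules could bear on the cohort:
- Section 3.1 stops enrolment at an untested dose if both of the first two patients have a DLE.
- Section 3.3.4.3 interrupts the trial for one serious, or two severe, drug-related reactions.
- The Bayesian logistic regression model (BLRM) is updated once the cohort is complete: "After all patients in a cohort have either experienced a DLE or have been observed for at least the 7 days evaluation period" is the stated trigger.

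**The concern.** The reviewers are told to look at the DLE data, but the rule for releasing patients 2 and 3 does not ask whether a DLE has occurred. A sentinel could lose more than 15 letters by day 4, have this recorded as a DLE, have it judged non-serious, and the written instruction would still be to dose the next two patients. In a first-in-human intravitreal trial the sentinel step exists so that someone decides before more eyes are exposed. At stake are up to two further patients in an affected cohort.

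**Working it through.** **Step 1: does another written rule hold dosing after one non-serious sentinel DLE?**
- The two-consecutive-DLE rule needs patient 2 to be injected and to have a DLE. It can spare patient 3 only if that DLE shows before patient 3 is dosed, and Section 3.1 sets no interval between the two.
- The stopping rule in Section 3.3.4.3 needs one serious or two severe related reactions.
- The BLRM update waits for the whole cohort.

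None of them acts.

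**Step 2: which DLEs can be both non-serious and evident by day 4?**
- Inflammation: needs 5 or more days, so it is not complete on day 4.
- Intraocular pressure: Section 6.2.2 places the injection "after the other ophthalmologic assessments in the" flow charts, so the first scheduled post-dose reading in Flow Chart I is the day-4 visit. Scheduled data cannot show 3 days' persistence.
- Vascular occlusion: can be seen by day 4 but may well be judged serious.
- Loss of more than 15 letters: acuity is tested at day 4 and a single reading suffices. This is the main case.

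**Step 3: what does the model say after a sentinel DLE?** Inputs are from Section 7.1: logit(p_d) = log α + β·log(d/d*), the three-component prior of Table 7.1:1, doses 0.5, 1 and 2.5 mg from Table 7.1:2, and the overdose-control (EWOC) limit P(OD) = P(p_d ≥ 0.25) < 0.25. The posterior is

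P(OD | data) = Σ w_i ∫ 1{p_d ≥ 0.25} L(θ) f_i(θ) dθ ÷ Σ w_i ∫ L(θ) f_i(θ) dθ, with L = Π p^r (1 − p)^(n − r),

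evaluated on a grid.

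The reference dose d* is redacted, so I solved for it from component 1: β = exp(0.0516) = 1.053; log(2.5/d*) = (logit 0.10 + 2.005)/β = (−2.197 + 2.005)/1.053 = −0.183; d* = 3.0 mg. The other two components give the same value. It remains an assumption, so I also ran 2.5 to 5 mg.

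Reproduction of the protocol's figures (Tables 7.1:2 and 10.2:1):

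| Case | Recomputed | Printed |
|---|---|---|
| Prior P(OD) at 0.5 / 1 / 2.5 mg | 0.117 / 0.162 / 0.290 | 0.117 / 0.164 / 0.286 |
| Scenario 2: 1 DLE in 3 at 0.5 mg | 0.344 | 0.345 |
| Scenario 4: 1 in 3 at 1 mg | 0.205 | 0.209 |
| Scenario 6b: 1 in 3 at 2.5 mg | 0.279 | 0.285 |
| Scenario 6c: as 6b, with 0 in 6 at 1 mg | 0.234 | 0.228 |

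Starting dose, P(OD) at 0.5 mg: 0.66 after 1 in 1, 0.47 after 1 in 2, 0.344 after 1 in 3 (0.350 to 0.329 over the d* range). After 1 in 3 the middle and top doses stand at 0.49 and 0.67, so no planned dose passes, and scenario 2 recommends stopping.

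**Step 4: do clean patients 2 and 3 still matter at the starting dose?** Section 4.1.3 permits intermediate or lower doses that meet EWOC, if the investigator and sponsor agree. I used 0.25 mg as an illustrative half dose:

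| Data | P(OD) at 0.25 mg | P(OD) at 0.5 mg |
|---|---|---|
| 1 in 1 at 0.5 mg | 0.570 | 0.663 |
| 1 in 3 at 0.5 mg | 0.233 | 0.344 |
| 1 in 3 at 0.5 mg, then 0 in 3 at 0.25 mg | – | 0.176 (0.182 to 0.162) |
| 1 in 1 at 0.5 mg, then 0 in 3 at 0.25 mg | – | 0.317 (0.327 to 0.295) |

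Two clean patients open a lower dose, and a clean cohort there brings the starting dose back inside EWOC. They are informative.

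**Step 5: how often?** The predictive probability of a sentinel DLE in the full 7 days, with earlier cohorts clean, is 0.09, 0.06 and 0.10 at 0.5, 1 and 2.5 mg. These are upper bounds on how often the gap would bite, because the documents give no share that is non-serious and evident by day 4.

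**The case against.** The strongest reply is that people already decide. Four roles must evaluate the DLE data and issue written minutes, the aim in Section 1.4.2.4 is to exclude acute events, DLEs are reported within 24 hours, and the SMC can modify or stop the trial (Section 8.7). All true, and a sensible group would probably pause. But this is discretion; the only written instruction for a non-serious event is that dosing proceeds.

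Second, the gap may be close to empty. A large loss of vision may qualify as serious through "Results in persistent or significant disability or incapacity", through the important-medical-event clause of Section 5.2.7.1.2, or through the sponsor's always-serious list (Section 5.2.7.1.3), which the documents do not reproduce. The SMC charter and Figure 3.1:1 are also unavailable. This limits the size of the point but does not remove the mismatch. One could also read the word serious in the release sentence as applying to systemic events only, in which case any ophthalmologic event would hold dosing. That is the less natural reading, and the ambiguity is itself a reason to reword.

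Third, a reader might infer from scenario 2 that patients 2 and 3 would be injected for nothing at the starting dose. The documents do not support this. Scenario 2 considers the planned doses only, and Step 4 shows that the lower doses allowed by Section 4.1.3 make those patients informative. Nor does the inference hold higher up: 1 in 3 passes at the middle dose, and scenario 6c returns to the top dose. A reader might also infer that the gate breaches EWOC. It does not, because Sections 3.1 and 7.1 use EWOC to choose the next cohort's dose, not to govern dosing within a cohort.

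**Conclusion.** The mismatch is real and of low severity. Section 3.1 reviews DLE data but conditions release on seriousness alone, and no other written rule covers a single non-serious sentinel DLE evident by day 4. Exposure is at most two further patients per affected cohort, at a frequency below the Step 5 probabilities by an amount the documents do not reveal. The argument for a hold is that a recorded decision should come before more eyes are dosed; it does not rest on those patients being uninformative.

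The textual finding needs no modelling. The starting-dose figure is the protocol's own. The lower-dose figures rest on d* = 3.0 mg and an illustrative 0.25 mg, and their conclusions hold over d* from 2.5 to 5 mg.

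Nothing here suggests harm to a participant or bias in a result: Protocol Section 1.2 reports 12 patients treated in the SRD part without a DLE, and SAP Section 6.1 confirms 12 enrolled with recruitment complete. The point matters if single dosing is reopened or the rule is reused.

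**What to change.** Reword the release condition in Section 3.1 along these lines: *Patients 2 and 3 are dosed only if the sentinel has had no serious adverse event, ophthalmologic or systemic, and no DLE under Section 5.2.1. After a sentinel DLE, their dosing is paused until the SMC documents a decision to continue or not.*

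This is a pause, not a stop. The requirement "For any dose-escalation cohort, at least 3 evaluable patients will be required" and the whole-cohort BLRM update can stay as they are. I do not propose a new rule for closing a cohort below three patients: the simulations in Section 10.2 use cohorts of 3 and do not cover it.

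The cost is two sentences and, if a sentinel DLE occurs, a short delay within the cohort. No visit, patient or SAP analysis is added.
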